4.2. Scientific Rationale for Study Design

As this is the first time ALXN1850 will be dosed in humans, an open-label dose escalating design was chosen for initial assessment of the safety, tolerability, PK, and PD of ALXN1850 IV and SC in adults with HPP.

The scientific rationale for each aspect of the study design is discussed below:

- This study will be conducted in adult participants with HPP because ALXN1850 is designed as a TNSALP ERT that is expected to lead to improvement in this patient population. Because of the potential for immunogenicity, this study will enroll adults with HPP who are not anticipated to require continued treatment with ERT, based on their signs and symptoms, and the Investigator's clinical assessment of their current condition.
- A single ALXN1850 IV dose will provide the reference necessary for assessing absolute bioavailability.
- Weekly SC dose will provide the PK and PD information that will support the intended dose regimen in this patient population.
- Three weekly doses of SC ALXN1850 will provide accumulation information for this study drug.
- The qw SC dose range proposed for this study (15 to 90 mg) is expected to cover the therapeutic range in humans.
- An 8-week follow-up will provide enough time to assess immunogenicity and possible risks to the participants.

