4.3. Justification for Dose

First-in--human dose selection was based on PK data collected from a wild-type mouse study; rat and monkey dose range finding studies; 4-week GLP toxicology studies in rats and monkeys; and efficacy data from 2 Akp2GW -/- mouse efficacy studies. A model-based approach employing dose response and population PK (PopPK) models was used to characterize the SC dose (15 mg [0.15 mL], 45 mg [0.45 mL], and 90 mg [0.90 mL]) after performing body weight-based forecasting to humans for the FIH study. A NOAEL based approach was used to determine the starting dose (15 mg IV). A summary of the expected exposure margin and- expected percentage of population with normalized mineralization response in humans for ALXN1850 is provided in Table 5. Given previous experience with asfotase alfa, it is expected that the ALXN1850 safety multiple will support flat dosing. The trade-off of flat dosing versus mg/kg dosing is some increase in PK variability (within a cohort) with a gain of reduction in potential errors in dosing and operational factors.

The 15 mg IV starting dose is considered the maximum recommended starting dose (MRSD). The starting dose was selected based on NOAEL from the 4-week GLP toxicology study in monkeys dosed SC q3d. Monkey was selected because it has relevant biology with humans. The monkey NOAEL was determined to be 20 mg/kg/q3d or 46 mg/kg/week. Assumptions of 1) no allometric scaling for a molecule with molecule weight > 100 kDa (Food and Drug Administration (FDA) guidance: Estimating the Maximum Safe Starting Dose in Initial Clinical Trials for Therapeutics in Adult Health Volunteers, 2005), 2) applying safety factor of 150, and 3) SC bioavailability (75%), 4) adult body weight of 70 kg, were factored into the calculation of the starting dose. Based on dose simulation results, the observed exposure of the NOAEL at 20 mg/kg/dose from the GLP monkey toxicity study is approximately 113-fold of projected exposure from the 15 mg IV starting dose (Table 5).

Cohort 1 will receive 15 mg as a single IV dose, followed by 15 mg SC at 1-week intervals for 3 doses. The 15 mg SC dose was calculated (based on dose-response modeling of mouse data) to produce normalized bone mineralization in 66% of a treated population.

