In addition, attainment of steady state will be assessed via stepwise, linear mixed regression models with a random subject effect among subsequent participants. The analysis will be stratified by cohort. This approach involves an examination of Ctrough concentrations over time using mixed regression models and calculating a slope and corresponding 95% CI. Predose assessments on day 8, day 15, and day 22 will be used. The model results will be evaluated to see if 0 is included in the 95% CI which indicates that the steady state was achieved.

Plasma PK concentrations of ALXN1850 will be reported to 3 significant figures in summary statistics except for %CV which will be reported to 1 decimal place and N and n which will be reported as integers.

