8.3. Plasma Pharmacokinetic Parameters

The plasma concentration-time data for ALXN1850 will be analyzed by non-compartmental analysis using Phoenix® WinNonlin® Version 8.0 or higher (Certara USA, Inc., Princeton, New Jersey). The following PK parameters will be derived for ALXN1850 based on actual date and times calculated relative to the actual date and time from the start of dose administration (for example, start of infusion) in each dosing period, where data permit. If missing actual sampling dates and times, then the nominal time relative to the start time of the administration will be used.

C _{max}	Maximum observed plasma concentration
C _{max_corrected}	Maximum observed plasma concentration (for SC dose only if carryover from IV exposure is observed)
C _{trough}	Trough (predose) concentration observed at the start of the dosing interval (C _{trough})
T _{max}	Time of maximum observed concentration
AUCt	Area under the curve (AUC) from time 0 to the last quantifiable concentration, calculated using the linear trapezoidal rule
AUC _{168h}	Area under the curve (AUC) from time 0 to 168h, calculated using the linear trapezoidal rule (for IV dose only)
AUC _{inf}	AUC from time 0 extrapolated to infinity, calculated using the linear trapezoidal method (IV dose only)
AUC _{tau}	AUC within the dosing interval, calculated using the linear trapezoidal method (SC dose only)
AUC _{tau_corrected}	AUC within the dosing interval, calculated using the linear trapezoidal method (for SC dose only if carryover from IV exposure is observed)
t _{1/2}	Apparent terminal elimination half-life, calculated as: ln (2) / Kel
CL	Total body clearance calculated as: Dose / AUC _{inf} (For IV dose only)
CL/F	Apparent total body clearance calculated as: Dose / AUC _{tau} at steady state (For SC dose and only if C _{trough} can attain steady state)
V_d	Volume of distribution during the terminal phase, calculated as: Dose / $[\lambda_z * AUC_{inf}]$ (For IV dose only)
V _d /F	Apparent volume of distribution during the terminal phase, calculated as: Dose / [λ_z * AUC _{tau} at steady state] (For SC dose and only if C _{trough} can attain steady state)
R	Subcutaneous accumulation ratio (AUC _{tau_SC} 3rd dose / AUC _{tau_SC} 1st dose)
F	Absolute bioavailability after subcutaneous administration, $F = AUC_{tau}$ (SC) / AUC_{inf} (IV)

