In addition to the above PK parameters, which will be listed and summarized, the following parameters will also be listed to document the selection of data points used to estimate $T_{1/2}$ using non-compartmental procedures:

λ_z	Terminal phase elimination rate constant
Number points	Number of data points used to estimate λ_z ; a minimum of 3 data points must be used, and C_{max} must not be included
λ_z lower	Lower bound used for the estimation of λ_z
λ_z upper	Upper bound used for the estimation of λ_z
Rsq	r^2 , the coefficient of determination (goodness of fit statistic); λ_z and all associated parameters will only be reported where $r^2 \ge 0.80$
%AUC _{extrap}	Percentage of AUC_{inf} due to extrapolation; If % $AUC_{extrap} > 20\%$ then, AUC_{inf} , CL, and V_d , will not be summarized

Additional plasma PK parameters may be calculated if deemed appropriate.

Plasma PK parameters for ALXN1850 will be presented in data listings and summarized separately using descriptive statistics (n, arithmetic mean, SD, %CV, geometric mean, geometric %CV, median, minimum, and maximum) by treatment. T_{max} will be summarized using the descriptive statistics median, minimum, and maximum only. Plasma PK will be presented by ADA status in figures. In addition, the Plasma PK parameters and ADA titers will be presented in the overlay figures for each subject overtime.

Plasma PK parameters of ALXN1850 will be reported to 3 significant figures in summary statistics except for %CV which will be reported to 1 decimal place and N and n which will be reported as integers.

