8.4. Pharmacokinetic Statistical Analyses

Dose-proportionality of plasma ALXN1850 PK parameters, C_{max} , AUC_{168h} , AUC_{inf} , (IV dose only), and AUC_{tau} (SC dose only) for both IV and SC treatments over the dose range tested will be investigated. A power model will be fitted to describe the relationship between Y (C_{max} , AUC_{168h} , AUC_{inf} , and AUC_{tau}) and X (dose) using the least squares linear regression model:

• $ln(Y) = ln(\alpha) + \beta ln(X)$, which is the logarithmic form of $Y = \alpha X^{\beta}$, where Y is PK parameter and X is dose.

The intercept of regression line, α , and the slope of the regression line, β , will be presented along with the 90% confidence interval (CI) of the slope. Dose proportionality will be concluded when the 90% CI of the slope (beta) lies entirely within $[(1+\ln(0.8)/\ln(r), 1+\ln(1.25)/\ln(r))]$, where r is the dose range (highest dose/lowest dose).

Dose-proportionality of plasma ALXN1850 PK parameters, C_{max}, AUC_{168h}, AUC_{inf}, (IV dose only), a nd AUC_{tau} (SC dose only) for both IV and SC treatments over the dose range tested will be investigated based on ADA status (ADA negative and ADA positive, and/or pre-existing immunogenicity, treatment-emergent ADA responses, and treatment-boosted ADA responses if data permits) usi ng a similar model.

Absolute bioavailability of ALXN1850 following SC administration will be assessed by comparing AUC_{tau} values of the first SC dose versus AUC_{inf} of the IV dose for the similar dose

cohorts. Log-transformed AUC_{tau} and AUC_{inf} estimates will be analyzed using an analysis of variance model with group (IV vs SC) as a factor. The parameter estimates results will be exponentiated and the ratio of geometric means and 90% CIs will be presented. Analysis will be repeated by ADA status.

9. Safety Analysis

All safety summaries and analyses will be based upon the Safety Set.

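### The SAP 8.4 bioavailability ANOVA names route as its only factor although each participant supplies both the IV and the SC AUC, so its 90% CI treats paired data as independent

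*SAP*

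**What the plan says.** Protocol section 4.2 gives the purpose of the IV dose: "A single ALXN1850 IV dose will provide the reference necessary for assessing absolute bioavailability". Section 4.3 gives the sequence within a person, for example "Cohort 1 will receive 15 mg as a single IV dose, followed by 15 mg SC at 1-week intervals for 3 doses". Cohorts 2 and 3 follow the same pattern at 45 mg and 90 mg.

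SAP section 8.4 log-transforms AUCtau (first SC dose) and AUCinf (IV), analyses them with an "analysis of variance model with group (IV vs SC) as a factor", exponentiates, and reports the ratio of geometric means with 90% CIs. The comparison is described as being within similar dose cohorts and is repeated by ADA status. Neither SAP 8.4 nor Protocol section 9.4.3.1 mentions a participant term, a repeated-measures structure or a paired contrast.

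SAP section 8.2 does write such a term out for the trough analysis: "attainment of steady state will be assessed via stepwise, linear mixed regression models with a random subject effect among subsequent participants".

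SAP section 8.3 also derives an individual F for each participant. PK parameters are listed and "summarized separately using descriptive statistics (n, arithmetic mean, SD, %CV, geometric mean, geometric %CV, median, minimum, and maximum) by treatment".

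**The concern.** An ANOVA with route as its only factor is a two-sample comparison. It builds the standard error from the between-participant spread in each arm, as though different people had received IV and SC. Here the same people received both, and much of that spread should cancel in the within-person ratio.

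Positive correlation between the two log-AUCs is plausible. Both depend on the same person's clearance. The protocol also accepts that "The trade-off of flat dosing versus mg/kg dosing is some increase in PK variability (within a cohort") will follow, and that source of variation acts on both routes in one person.

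Absolute bioavailability is a secondary objective, and this is the only CI planned for it. What is at stake is whether an interval labelled 90% covers 90%. Because SAP 8.2 spells out a subject effect, a programmer cannot safely assume that 8.4 intends one.

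**Working it through.** The plan states no precision figure for this analysis, so there is none to reproduce.

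**Inputs.** Confidence level 90% (SAP 8.4). Participants per cohort: about 5 planned (Protocol 1.1), at least 3 completing (SAP 4.2). The documents give neither the correlation rho between the IV and SC log-AUCs nor their SDs. I assume rho from 0 to 0.9 and SD ratios of 1, 2 and 3.

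**Formulas**, for n complete pairs:
- Half-width as planned: t(0.95, 2n−2) × √((s_IV² + s_SC²)/n)
- Paired half-width: t(0.95, n−1) × s_d/√n, where s_d is the SD of the within-participant log differences
- True variance of the mean log difference: (σ_IV² + σ_SC² − 2·rho·σ_IV·σ_SC)/n

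The planned model omits the last term of the true variance. With equal variances it estimates 2σ²/n when the truth is 2σ²(1−rho)/n, an overstatement by a factor 1/(1−rho): 2.0 at rho 0.5 and 3.3 at rho 0.7. Against that, the t multiplier is smaller: 2.132 against 2.920 at n=3, and 1.860 against 2.132 at n=5.

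**Coverage of the planned 90% CI, equal variances** (400,000 bivariate-normal trials per setting; simulation error about 0.1 point):

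| rho | n=3 | n=4 | n=5 |
|---|---|---|---|
| 0 | 90.1% | 90.0% | 89.9% |
| 0.25 | 92.8% | 93.2% | 93.5% |
| 0.5 | 95.4% | 96.2% | 96.5% |
| 0.7 | 97.4% | 98.1% | 98.5% |
| 0.9 | 99.2% | 99.6% | 99.8% |

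At rho −0.3, coverage is 86.2% (n=3) and 85.6% (n=5), so the direction of the error depends on the sign of rho.

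**Mean width, planned over paired, equal variances:**

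| rho | n=3 | n=4 | n=5 |
|---|---|---|---|
| 0.25 | 0.89 | 0.99 | 1.04 |
| 0.5 | 1.08 | 1.21 | 1.26 |
| 0.7 | 1.38 | 1.55 | 1.62 |
| 0.9 | 2.35 | 2.64 | 2.78 |

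Mean widths are equal at rho of about 0.41 (n=3), 0.27 (n=4) and 0.19 (n=5).

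**Coverage of the planned CI, unequal variances:**

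| SD ratio, n | rho 0 | rho 0.1 | rho 0.3 | rho 0.5 |
|---|---|---|---|---|
| 2, n=3 | 88.5% | 89.4% | 91.4% | 93.0% |
| 2, n=5 | 88.9% | 90.2% | 92.4% | 94.4% |
| 3, n=3 | 86.8% | 87.6% | 88.9% | 90.4% |
| 3, n=5 | 87.9% | 88.8% | 90.6% | 92.2% |

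Two things cause the shortfall. First, the pooled degrees of freedom are too many: at SD ratio 3 and n=3, the Satterthwaite value is (1+9)²/((1+81)/2) = 2.4, against the 4 used. Second, the omitted covariance is a smaller share of the variance: 2·3/(1+9) = 0.6·rho, against 1.0·rho with equal SDs.

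The paired CI covered 90% to within simulation error in every setting. All of this is coverage of the ratio of the AUCs entered. It does not address whether that ratio equals true bioavailability after carryover or truncation.

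**The case against.** The strongest reply is that little turns on this interval. With complete pairs the ratio of geometric means is identical under either model. There are no hypotheses, the sample size is empiric, and dose escalation rests on safety data and exposure limits; the only acceptance criterion in SAP 8.4 is for dose proportionality. All of this stands, and it limits the severity.

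The paired information is also already planned. From the n, geometric mean and geometric %CV of individual F, a reader can compute SD(log F) = √ln(1 + CV²) and then GM × exp(± t(0.95, n−1) × SD/√n). That stands too, but the CI actually reported for the endpoint would still be the unpaired one.

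Three stronger readings are tempting, and the documents do not support them.
- A reader might infer that the CI is certain to over-cover, or that any error is conservative. That needs positive correlation and similar variances, and neither is documented.
- A reader might infer that pairing will tighten the interval. At n=3 and rho 0.5 the paired CI is narrower in only 52% of simulated trials.
- A reader might infer that the estimate itself shifts because AUCinf values with more than 20% extrapolation are lost, leaving different people in each arm. SAP 8.3 says that AUCinf, CL and Vd "will not be summarized" in that case. It does not name F and does not say that these values leave the ANOVA.

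**Conclusion.** The point holds as a gap in the specification of the model's error structure. As written, SAP 8.4 fits an unpaired model to paired data, and nothing else in the documents adds the missing term.

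With similar log-scale variances, the nominal 90% CI covers about 93 to 97% (n=3) or 93 to 98.5% (n=5) for correlations of 0.25 to 0.7, and has its stated coverage only when the correlation is zero. With SDs differing two- to three-fold and weak correlation, coverage falls to about 87 to 89%. Which case applies cannot be settled from the documents. The figures rest on bivariate normal log-AUCs, complete pairs and analysis by cohort.

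The consequence is a mislabelled interval on a secondary endpoint. It is not a biased estimate, and no decision is affected. It should be corrected because the correction is simple and the planned interval does not match the design.

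**What to change.** In SAP 8.4, add participant to the bioavailability ANOVA and state that the model is fitted by cohort. Use a fixed participant effect if all pairs are complete; this is the t interval on within-participant log ratios (first-dose SC AUCtau over IV AUCinf) with n−1 df, exponentiated. If some participants have only one of the two AUCs, specify a random participant effect, because a fixed effect would take nothing about the ratio from them and the two analyses would then differ.

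The cost is a sentence or two of SAP text and no new data. The statistical price is that error df fall from 2n−2 to n−1 (4 to 2 at n=3; 8 to 4 at n=5). With equal variances the interval is therefore wider on average when rho is below about 0.41 (n=3), 0.27 (n=4) or 0.19 (n=5).

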9.1. Adverse Events

An adverse event (AE) is any untoward medical occurrence in a participant or clinical investigation participant administered a pharmaceutical product and which does not necessarily have to have a causal relationship with this treatment. An AE can therefore be any unfavorable and unintended sign (including an abnormal laboratory finding), symptom, or disease (new or exacerbated) temporally associated with the use of study intervention, whether or not considered related to the study intervention.

Adverse events will be analyzed in terms of TEAEs which are defined as any AEs that begin or worsen on or after the first dose of treatment until the final follow-up visit. If the onset date/time of an AE is missing and AE end date is on or after the first dose of treatment, the AE will be defined as treatment-emergent.

A treatment-related TEAE is defined as a TEAE that is considered to be related to the treatment.

A serious AE (SAE) is defined as any untoward medical occurrence that, at any dose, results in death, is life-threatening, requires inpatient hospitalization or prolongation of existing hospitalization, results in persistent disability/incapacity, is a congenital anomaly/birth defect, or are other situations (medical or scientific judgment should be exercised in deciding whether SAE reporting is appropriate in other situations such as important medical events that may not be immediately life-threatening or result in death or hospitalization but may jeopardize the participant or may require medical or surgical intervention to prevent one of the other outcomes listed in the above definition. These events should usually be considered serious).

The AE's relationship to study treatment will be evaluated by the investigator. The following relationships will be collected on eCRF: related or not related.

The AEs that are evaluated as related will be considered treatment-related AEs for summary purpose.

The severity of AEs will be classified by the investigator as mild (Grade 1), moderate (Grade 2), severe (Grade 3), 1 ife-threatening (Grade 4), or fatal (Grade 5).

Injection/infusion-site reactions are defined as AEs localized to the site of IV or SC route of study drug administration, occurring at any time during study participation that are assessed by the Investigator to be related to study drug.

Injection/infusion-associated reactions are defined as systemic AEs (eg, fever, chills, flushing, alterations in heart rate and blood pressure, dyspnea, nausea, vomiting, diarrhea, and generalized skin rashes) oc curring during or within 24 hours of the start of IV or SC injection/infusion that are assessed by the Investigator to be related to the study drug.

An overview summary of TEAEs will be provided and will include number and percentage of participants:

- With at least 1 TEAE
- With at least 1 TEAE related to study drug
- With at least 1 TESAE
- With at least 1 TESAE related to study drug
- Drug withdrawn due to a TEAE
- Drug withdrawn due to a TEAE related to study drug
- Who died
- With at least 1 injection/infusion-site reactions
- With at least 1 injection/infusion-associated reactions
- With at least 1 hypersensitivity reaction

All AE summary tables will be summarized by the most recent type of administration (IV or SC), cohort, and overall (within each cohort and all cohorts combined)

All AEs will be coded using MedDRA (version to be delineated in the CSR). The summary will be presented according to the most recent type of administration (ie, IV or SC) be ing received prior to the AE onset regardless of when the AE ended, and by cohort and overall.

The TEAEs will also be summarized by system organ class (SOC), p referred term (PT), by severity and relationship to study treatment. The TESAEs will also be summarized by SOC, PT, and by relationship to study treatment.

Adverse events of special interest including injection/infusion-site reactions and hypersensitivity including anaphylaxis (injection/infusion-associated reactions [IAR] + hypersensivity) will also be summarized by SOC and PT.

The summary of TEAE, TESAE, and AE of special interest including injection/infusion-site reactions and hypersensitivity including anaphylaxis by SOC and PT will also be repeated by ADA status (ADA negative and ADA positive, and/or pre-existing immunogenicity, treatment-emergent ADA responses, and treatment-boosted ADA responses if data permits).

In the summary tables where both SOC and PT are presented, the default ordering of SOC will be alphabetical and the default ordering for PT will be most prevalent (using percentage) PT within each SOC based on Total column. For PTs with the same number of participants, they should be further sorted by number of events and then alphabetically.

All summary tables will include number and percentage of participants and number of events, unless otherwise stated. For the number of AEs, each occurrence will be counted once. Percentages will be based upon the number of participants in the Safety Set.

In the by participant analyses, a participant having the same event more than once within the same level of summarization will be counted only once within the same administration (ie, IV or SC) using the most intense or severe event (for by toxicity grade summary) or the most related event (for by relationship summary).

All AEs will be listed from the signing of the ICF until the final follow-up visit.

Treatment-emergent AEs, TESAEs, TEAEs resulting in withdrawal from the study, injection/infusion-site reactions, hypersensitivity including anaphylaxis will be listed separately.

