Intervention Groups and Duration: The planned study duration for each participant is up to 22.5 weeks (approximately 5 months) in total: up to 8 weeks for Screening, 71 days for first participants and 63 days for subsequent participants for the Treatment Period, and 34 days for the post-dosing Follow-up Period to further monitor safety/tolerability, PK/PD, and immunogenicity. Dosing will be staggered within and between cohorts. The end of study is anticipated to be Day 85 (-7/+14 days) for the first participant in each cohort and Day 78 (-7/+14 days) for subsequent participants in each cohort.

[figure not shown]
Safety Review Committee: A SRC will assess all available data and will provide recommendations for cohort clearance and dose escalation decisions.

	Page 15 of 97	
A	lexion Confidential	

Protocol Amendment 5 10 Mar 2022 ALXN1850-HPP-101

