9.4.2. Safety Analyses

The primary objective of the study is to assess the safety and tolerability of ALXN1850. The endpoints to support the primary objective include incidence of TEAEs and treatment-emergent serious adverse events (TESAEs). The incidence of TEAEs and TESAEs will be summarized by System Organ Class (SOC) and Preferred Term by administration and cohort overall, by severity, and by relationship to study intervention. Adverse events will be categorized by the type of administration being received at the date of onset (ie, IV or SC). Treatment-emergent AEs and TESAEs resulting in withdrawal from the study will be listed. Participants having multiple AEs within a category (eg, overall, SOC, Preferred Term) will be counted once in that category. For severity tables, a participant's most severe event within a category will be counted. Adverse events of special interest will be analyzed similarly.

Changes from baseline in vital signs and laboratory assessments (as displayed in Table 7) will be summarized by visit for each cohort. Laboratory parameter values will be graded based on the National Cancer Institute CTCAE grading for severity (v5.0, published 27 Nov 2017). Shift tables by treatment group will be produced for these laboratory parameters. These tables will summarize the number of participants with each baseline grade relative to the normal ranges and changes to the worst highest grade assessed postdose during the study.

Electrocardiogram parameters will be measured at the specified time points, including heart rate, PR, RR, QRS, QT, and QTcF intervals. The average of the triplicate ECG readings at the time points collected will be calculated, and changes from pretreatment baseline values will be assessed.

An outlier analysis will be performed that will summarize the frequency and percentage of participants who meet any of the following outlier criteria at each visit.

- QT, QTcF interval > 450 msec
- QT, QTcF interval > 480 msec
- QT, QTcF interval > 500 msec
- QT, QTcF interval increases from baseline > 30 msec
- QT, QTcF interval increases from baseline > 60 msec

Physical examination results will be classified as Normal, Abnormal Not Clinically Significant (NCS), Abnormal Clinically Significant (CS), and Not Examined. The results will be summarized by visit for each administration.

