Absolute, change, and percent change from the baseline in mean plasma PLP, PLP/PL ratio, and PPi concentration versus time data will be presented graphically by cohort and by ADA status (ADA negative and ADA positive, and/or pre-existing immunogenicity, treatment-emergent ADA responses, and treatment-boosted ADA responses if data permits) over timepoints relative to dose for all participants. This mean figure will be repeated including all participants up to 1 week post IV dose and subsequent participants for the remaining relative time to dose. In addition, the value of plasma PLP, PLP/PL ratio, and PPi for each participant will be presented graphically overlaid with ADA status over timepoints relative to dose.

All data for PPi, PLP, and PL will be presented in data listings.

11. Immunogenicity Analysis

All immunogenicity analyses will be performed on the Immunogenicity Analysis Set.

Asfotase alfa ADA and NAb will only be tested in participants who have previously received asfotase alfa. Immunogenicity analyses (ALXN1850 ADA and NAb) will be performed on samples collected at timepoint shown below:

First participant within each cohort	Subsequent participants within each cohort
Day 1 (pre IV dose)	Day 1 (pre IV dose)
Day 8 (1 week post IV dose)	
Day 15 (pre SC dose 1)	Day 8 (pre SC dose 1)
Day 22 (pre SC dose 2)	Day 15 (pre SC dose 2)
Day 29 (pre SC dose 3)	Day 22 (pre SC dose 3)

Page 25 of 29

First participant within each cohort	Subsequent participants within each cohort
Day 36 (1 week post SC dose 3)	Day 29 (1 week post SC dose 3)
Day 51 (3 weeks post SC dose 3)	Day 43 (3 weeks post SC dose 3)
Day 65 (5 weeks post SC dose 3)	Day 57 (5 weeks post SC dose 3)
Day 85/ED/EoS (8 weeks post SC dose 3)	Day 78/ED/EoS (8 weeks post SC dose 3)

Immunogenicity testing (asfotase alfa ADA and NAb) will be performed at Screening for participants who have previously received asfotase alfa.

Anti-drug antibody variables include ADA response category incidence and titer over the duration of the study will be defined as:

- ADA negative: ADA negative response in the ADA assay at all time points.
- ADA positive: include participant with a positive response in the ADA assay at any time point will be categorized as follows:

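### TEAE percentages by route set one IV dose and 7 to 14 days against three SC doses and 70 days, over a single Safety Set denominator

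*SAP*

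**What the plan says.** Four rules together fix what the route columns contain.

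- **Attribution.** SAP Section 9.1: "All AE summary tables will be summarized by the most recent type of administration (IV or SC), cohort, and overall". An event goes to the last route given before its onset. Protocol Section 9.4.2 likewise splits events by the route in use at onset.
- **Collection period.** The same SAP section counts as treatment-emergent the events that "begin or worsen on or after the first dose of treatment until the final follow-up visit". There is no cut-off after the last dose.
- **Denominator.** SAP Section 9.1: "Percentages will be based upon the number of participants in the Safety Set". SAP Section 4.4 admits to that set anyone given any amount of study drug. The general rule in SAP Section 4 also uses the cohort size in the population of interest.
- **Calendar.** Protocol Table 3 places the first SC dose on Day 15 for the first participant in a cohort and on Day 8 for the others. The Protocol synopsis puts the end of study at "Day 85 (-7/+14 days) for the first participant in each cohort and Day 78 (-7/+14 days) for subsequent participants in each cohort".

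Participants count once per event level within each route, and event counts are shown beside the percentages. Neither document plans an exposure-adjusted rate, a matched post-dose window or a note on unequal follow-up for the AE tables.

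**The concern.** TEAE and TESAE incidence is the primary endpoint, and the primary objective names both routes, so readers will look across from the IV column to the SC column. Those columns differ in length of observation and in number of doses before any effect of route comes in. The event counts carry the same imbalance. A reader could take a higher SC percentage as a sign of poorer SC tolerability, and SC is the route for which the product is designed.

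The denominator is a second and separate problem. A participant who stops between the IV dose and the first SC dose cannot contribute an SC event but is still counted under SC. "Study drug received" in SAP Section 4.4 does not resolve this, because both routes deliver the same drug.

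Elsewhere the SAP does attend to time since dose. Laboratory, vital-sign and ECG results are summarised by time relative to dose, and SC pharmacokinetic parameters are corrected where IV carryover is seen. The AE tables have no counterpart.

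**Working it through.** **Check of the calendar.** SAP Section 9.3 labels the final visit as 8 weeks after SC dose 3. First participants: 85 − 29 = 56 days. Subsequent participants: 78 − 22 = 56 days. Both are 8.0 weeks, so the label reproduces. Taking off the 7-day dosing interval leaves 49 days, or 7 weeks.

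**Windows.**
- IV, first participant: 15 − 1 = 14 days. IV, subsequent: 8 − 1 = 7 days.
- SC, first: 85 − 15 = 70 days. SC, subsequent: 78 − 8 = 70 days. The end-of-study visit window (−7/+14) makes this 63 to 84 days.
- Per cohort of 5: IV 14 + 4 × 7 = 42 participant-days; SC 5 × 70 = 350.
- For 15 participants: IV 126; SC 1,050; ratio 8.3.

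**Expected incidence with no route effect.** The documents give no background event rate. I assume one constant daily rate λ for both routes, set by the 30-day incidence r: λ = −ln(1 − r)/30. Incidence over t days is 1 − exp(−λt). The IV figure averages 3 participants at 14 days and 12 at 7 days.

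At r = 20%, λ = 0.00744 per day. IV is 9.9% over 14 days and 5.1% over 7 days, averaging 6.0%. SC over 70 days is 40.6% (37.4% at 63 days, 46.5% at 84).

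| Assumed 30-day incidence | IV | SC | P(SC count > IV count), N = 15 | Same, cohort of 5 |
|---|---|---|---|---|
| 5% | 1.4% | 11.3% | 0.77 | 0.43 |
| 10% | 2.9% | 21.8% | 0.92 | 0.65 |
| 20% | 6.0% | 40.6% | 0.99 | 0.85 |
| 30% | 9.5% | 56.5% | 0.998 | 0.92 |
| 50% | 17.5% | 80.2% | >0.999 | 0.98 |
| 80% | 35.6% | 97.7% | >0.999 | 0.99 |

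The probabilities are exact binomial convolutions that treat the two route counts as independent. In a cohort of 5 the remainder is mostly ties (0.54 at 5%, 0.31 at 10%). SC falls below IV with probability at most about 0.04.

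**If risk comes only from doses.** With equal risk q per dose, IV shows q and SC shows 1 − (1 − q)³. For q = 5, 10, 20, 30 and 50%, SC is 14, 27, 49, 66 and 88%. The ratio falls from 2.9 to 1.8.

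**Denominator.** At r = 20%, suppose 3 of 15 never reach SC. The Safety Set denominator gives 12/15 × 40.6% = 32.5%; the 12 participants dosed SC give 40.6%. IV is held at 6.0% here.

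**Rate per participant-week.** At the same λ, expected IV events are 126 × 0.00744 = 0.94 over 18 participant-weeks, or 0.052 per week. Expected SC events are 1,050 × 0.00744 = 7.81 over 150 participant-weeks, also 0.052.

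**The case against.** The best reply is that no IV-versus-SC safety comparison is planned. Both documents state that there are no hypotheses, and Protocol Section 4.2 includes the IV dose as the bioavailability reference. Each AE table also has overall columns within and across cohorts, so the primary endpoint is reported without the route split. Escalation and stopping rest on committee review and participant-level triggers (Protocol Sections 6.6 and 7.1), not on the two route percentages. All AEs are listed, which with about 15 participants lets a reader check timing. Crediting late events to SC can be defended as cautious.

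Most of this stands and limits the point. It does not make the route columns readable: with no test, the displayed percentages are the result, and a listing does not correct a table.

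Some stronger readings go beyond the documents:

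- *That the primary analysis is biased.* The overall columns are not affected.
- *That SC must look worse in every table.* It is expected to, but at low rates a cohort of 5 often ties, and a true excess of IV reactions could be masked. Rows for single preferred terms or serious events would usually have low rates.
- *That the last seven weeks are drug-free.* The amendment history justifies the end-of-treatment visit as 5.5 half-lives. Counted from SC dose 3 (Day 22 to Day 57, 35 days), that implies a half-life near 6.4 days, so roughly half the drug would remain one week after the last dose.
- *That the imbalance in days applies to every event type.* Injection/infusion-associated reactions are limited to 24 hours from the start of a dose, so there it is three doses to one.
- *That the denominator adds to the SC excess.* It works the other way, and only if someone stops before SC dose 1. AE table shells are not among the documents and might define it differently; the SAP text does not.

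**Conclusion.** The point holds as a descriptive interpretation bias confined to the route columns. The windows and the 8.3-to-1 ratio follow from the schedule alone. The percentages rest on an assumed constant background rate common to both routes. Across 30-day incidences of 5% to 80%, expected SC incidence is 2.7 to 7.9 times expected IV incidence; under dose-only risk it is 1.8 to 2.9 times. The direction is the same throughout, but the size cannot be known before the event rates are. The denominator problem is real, smaller and opposite in sign: in the example it moves SC from 40.6% to 32.5%, still far above 6.0% for IV, so it does not cancel the main effect. It is worth correcting because, followed as written, the plan would show different route percentages for the primary endpoint where there is no route effect.

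**What to change.** In SAP Section 9.1:

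1. Keep n (%) and the overall columns.
2. State that SC percentages use participants who received at least one SC dose.
3. Add events per participant-week at risk by route. Compute time at risk from actual dose and last-visit dates, so that follow-up of anyone who never starts SC counts under IV.
4. Footnote each route table with the scheduled windows: IV one dose, 7 days (14 for first participants); SC three doses, 70 days.

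The rate should sit beside n (%), not replace it. It equalises the columns only if risk is constant over time. If risk came only from doses, it would favour SC: with 15 participants, 15q/18 = 0.83q IV events per week against 45q/150 = 0.30q for SC. The footnote lets the reader weigh both figures. IV time is also short, at 6 participant-weeks per cohort of 5, so its rate will be imprecise.

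The cost is a few SAP sentences and slightly larger tables. Dose and onset dates are already needed for the planned attribution, so nothing changes in study conduct.
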